7.6 Analysis of PK

PK/PD analyses will be provided in a separate report.

7.7 Subgroups of Interest

The primary efficacy endpoint summaries will be repeated by smoking status (current vs. former/never). The subgroup analyses for CYP1A2 inducers / inhibitors may be performed if data is available.

7.8 Other Analyses

Pharmacogenomic samples will be collected. Data will be analyzed and reported separately.

7.9 Interim Analysis (and Early Discontinuation of the Clinical Study)

An early timepoint analysis is planned 4 weeks after the last randomization. The unblinded results will be restricted to a very small group independent of the study team. No changes to the study or the statistical analysis plan will be made as a result of this analysis (which is intended to assist with internal decision making only). Full details will be documented in a separate charter to ensure the integrity of the trial blinding; all study team personnel, including all those involved in data management, clinical, medical or statistical review of the data, will remain blinded until database hard-lock (see Section 3.3).

7.10 Handling of Missing Data, Outliers, Visit Windows, and Other Information

7.10.1 Missing Data

If there are no diary entries for a particular calendar day, and the patient reported receiving at least one morning dose of study medication or at least one evening dose of study medication on that day, the frequency of vasomotor symptoms will be imputed to 0; otherwise, the frequency of vasomotor symptoms will be considered missing.

If no vasomotor symptoms were recorded for the day, and the patient reported receiving at least one morning dose of study medication and at least one evening dose of study medication on that day, the severity will be 0.

Missing primary endpoints will be handled by multiple imputation for continuous variables, and non-responder imputation for binary variables.

For study drug compliance, the capsules returned will be imputed to 0 at the visit if no bottle was returned for a visit.

Multiple Imputation Method:

Multiple imputation will be used to impute missing data and will be implemented using SAS® PROC MI. Missing data may be the result of missing Week 4/Week 12 frequency/severity of vasomotor symptoms measurements or the result of patients discontinuing treatment prior to Week 4/Week 12. Missing at random will be assumed.

The imputation model will include the subject demographics (age [$<$ median, \geq median], race [white, non-white], baseline weight [$<$ median, \geq median], and smoking status), and baseline and post-baseline frequency/severity of vasomotor symptoms. Missing data will be imputed 100 times to generate 100 complete data sets. The seed will be 98765. The fully conditional specification method will be used. The 100 complete data sets will then be analyzed using the same analysis method as the one used to analyze the primary endpoint. See Section [7.4.1.1](#). The results from the 100 fitted models will be combined using SAS® PROC MIANALYZE.

If the model fails to converge, exclusion of subject demographics will be considered.

Safety Data Imputation:

As a general principle, no imputation of missing data for other variables will be done. Exceptions are the start and stop dates of AEs and concomitant medication in rare cases. The imputed dates will be used to allocate the concomitant medication and AEs to a treatment period, in addition to determining whether an AE is/is not treatment emergent. Listings of the AEs and concomitant medications will present the actual partial dates; imputed dates will not be shown.

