Subjects who are withdrawn from the study prior to completion of the scheduled study procedures for any reason (adverse event, withdrawal of consent, etc.) should be invited to complete the ET assessments (see Section 6.5). As long as the subject consents, all relevant assessments of the day on which the subject withdrew from the study should be completed (at a minimum those related to safety) and the subject should return for a safety follow-up visit approximately 3 weeks after the last intake of study drug. As long as the subject consents, she will be asked to continue the completion of the eDiary up to the safety follow-up visit. In case of an adverse event, the appropriate follow-up will be done.

Subjects who are withdrawn from the study will not be replaced.

Study drug assigned to a withdrawn subject must not be assigned to another subject.

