8 EFFICACY AND OTHER ASSESSMENTS

8.1 Efficacy Assessments

8.1.1 Hot Flash Frequency and Severity

Subjects will record vasomotor symptom frequency and severity of each vasomotor symptom on an ad hoc basis, but at a minimum twice daily (morning and evening), via the ePRO diary from the screening visit (Days -35 to -1 [Visit 1]) through the follow-up visit (Week 15 [Visit 6]). At the screening visit, subjects will receive the ePRO diary in which to record daily vasomotor symptoms during the screening period. Subjects must have ≥ 7 consecutive days of vasomotor symptom recordings to participate in the study. Data on vasomotor symptom frequency and severity collected during the screening period (Days -35 to -1) will serve as baseline for vasomotor symptom frequency and severity. Vasomotor symptoms will be recorded by calendar day (ie, 1 day is midnight [12:00 AM (00:00 hours)] to 11:59 PM [23:59 hours]).

Night sweats (vasomotor symptoms that disrupt the subject's night sleep) should be recorded no later than in the morning upon awakening to start a new day. Subjects should take note of the time of the night sweat and record it on the appropriate calendar day (ie, before or after midnight).

The severity of vasomotor symptoms is defined clinically as follows (according to the FDA and European Medicines Agency Guidances for Industry^{23,24} and the National Institutes of Health [NIH] Hot Flash Workshop²⁵):

- Mild: Sensation of heat without sweating/dampness. If at night, subject does not wake up but later notices damp sheets or clothing.
- Moderate: Sensation of heat with sweating/dampness, but able to continue activity. If at night, subject wakes up because she is feeling hot and/or is sweating, but no action is necessary other than rearranging the bed sheets.
- Severe: Sensation of intense heat with sweating, causing disruption of activity. If at night, subject wakes up hot and is sweating and needs to take action (eg, remove layers of clothes, open the window, or get out of bed).

The definition of the main parameters are as follows:

Frequency

The frequency is the number of vasomotor symptoms per day.

Severity

Severity of moderate to severe vasomotor symptoms per day is calculated as follows:

$$\frac{[(\text{number of moderate vasomotor symptoms} \times 2) + (\text{number of severe vasomotor symptoms} \times 3)]}{\text{number of daily moderate/severe vasomotor symptoms}}$$

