7.4.2 Analysis of Secondary Endpoints

The analysis of secondary efficacy endpoints will be based on the FAS.

For each of the secondary vasomotor symptom and patient-reported outcome endpoints, an MMRM model as described in Section 7.4.1.2 will be used. The treatment difference will be estimated at all study weeks (week replaced by visit for patient-reported outcome endpoints).

For each of the secondary responder endpoints, logistic regression will be used for the analysis for each week and endpoint. The analyses will include the treatment group and smoking status (current vs. former/never) as factors and baseline measurement (mean frequency of vasomotor symptoms) as a covariate. The missing value will be imputed as a non-responder.

[figure not shown]
For these responder endpoints, the number of subjects who achieve the reduction will be summarized by study week with descriptive statistics for each treatment arm. For 50% and 90% reduction responders, Kaplan-Meier estimate will be used to estimate the time to response and the time to sustained response. Smooth average (SA) will be used for the time to response. SA value for day X-1, day X and Day X+1 would be assigned to day X. The time to response will be the first day with at least 50% (or 90%) response for both original numbers and SA number. The time to sustained response will be the first day with at least 50% (or 90%) response for both original numbers and SA number, and SA response from that day till the end of the treatment at least 50% (or 90%) response on each day. For the non-responders, it will be censored at the end of treatment.

Diary interaction compliance will be summarized with descriptive statistics and presented by treatment group.

Plasma concentrations of hormones and bone turnover markers will be summarized with descriptive statistics for each treatment group at each visit. Additionally, a within-subject change will be calculated as the post-baseline measurement minus the baseline measurement and summarized in the same way. Pharmacodynamic data and efficacy data may be evaluated by a population PD or population PK/PD approach. All details of population analyses will be described in a separate analysis plan and a separate report will be written. When deemed necessary, data from this study may be combined with data from other studies.

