7.10.6.1 Efficacy Visit Windows

For the weeks on treatment (weeks prior to the follow-up period), the last day is always the last day of exposure to treatment.

The study week determination for the vasomotor symptoms data is based on the following:

Analysis study week	Actual assessment day
Baseline	7 non-missing days prior to D1
Week 1	D1 to D7
Week 2	D8 to D14
Week 3	D15 to D21
Week 4	D22 to D28
Week 5	D29 to D35
Week 6	D36 to D42
Week 7	D43 to D49
Week 8	D50 to D56
Week 9	D57 to D63
Week 10	D64 to D70
Week 11	D71 to D77
Week 12	D78 to D84 or last day of exposure to treatment, if this happened after day 84
Last on Treatment Week	Last 7 days of treatment
Follow-up Week 1	Day 1 FU – Day 7 FU ^
Follow-up Week 2	Day 8 FU – Day 14 FU ^
Follow-up Week 3	Day 15 FU – Day 21 FU ^

^ Day X FU is defined as last day of exposure to treatment + X

The assessment of a week will be derived if any information for 3 or more days was reported (morning dose, evening dose, or vasomotor symptom).

All other efficacy assessments, including those from unscheduled visits and regardless of visit label, will be allocated to analysis visits based on the table below:

CRF visit	Target day	Actual assessment day	Analysis visit
Visit 1	D-35	D-35 to D-1	Screening
Visit 2	D1	D1	Baseline
Visit 3	D29	D22 to D36	Week 4
Visit 4	D57	D50 to D64	Week 8
Visit 5	D85	D78 to Day 92	Week 12
End of treatment	Last dosing day	Closest observation to the date	EOT
Visit 6	D106	Last assessment after date of completion or termination of treatment period	Week 15 Follow-Up

The value which assessment day is the closest to the defined target day within these windows is used. If two values are equally close, the latter is used in the analysis.

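### The SAP credits a symptom-free day only when a dose was reported, so symptom-free follow-up weeks are not derived and may be scored as non-response

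*SAP*

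**What the plan says.** SAP 7.10.1 sets the rule for days without diary data. Its condition reads "If there are no diary entries for a particular calendar day, and the patient reported receiving at least one morning dose of study medication", or an evening dose. In that case "the frequency of vasomotor symptoms will be imputed to 0; otherwise, the frequency of vasomotor symptoms will be considered missing". Severity is stricter: it needs a morning dose and also "at least one evening dose of study medication on that day, the severity will be 0".

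SAP 7.10.6.1 sets the minimum for a weekly value, which "will be derived if any information for 3 or more days was reported (morning dose, evening dose, or vasomotor symptom"). The same rule stands in SAP 6.1.1, which takes the weekly value as the mean of the data over 7 days.

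The analysis study-week table in SAP 7.10.6.1 lists Follow-up Weeks 1-3 and counts their days from the last day of exposure. SAP 6.1.2.1 and 6.1.2.2 define the secondary symptom and responder endpoints for each study week. SAP 7.4.2 estimates MMRM differences at all study weeks, and for the responder models says: "The missing value will be imputed as a non-responder".

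The diary runs through Visit 6. Protocol 8.1.1 asks for recording "at a minimum twice daily (morning and evening), via the ePRO diary", and Protocol 4.4 says of a withdrawn woman that "she will be asked to continue the completion of the eDiary up to the safety follow-up visit". Neither document gives a separate rule for off-drug days, and SAP section 8 lists no change on this point.

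**The concern.** On treatment, the dose record shows that the diary was in use, and a silent day with a dose can fairly be read as zero. Off drug that evidence disappears, but the rule still asks for it. Days then become missing because the outcome was good.

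Two things are at stake. First, a woman with no symptoms in a follow-up week has the best possible outcome, yet she has no weekly value and may be counted as a failure. Second, if the mean is taken over non-missing days, only days with at least one symptom enter it. The error grows as symptoms fall, so it differs between arms whenever their off-drug symptom levels differ. The missing-at-random basis of the MMRM is also doubtful for these weeks, because missingness is driven by the unobserved low value itself.

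**Working it through.** No figure in the documents belongs to this point, so there is none to reproduce. The first step is logic; the rest is illustration under stated assumptions.

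**1. The rules side by side**

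| Rule | On drug | Follow-up Weeks 1-3 |
|---|---|---|
| No entry gives frequency 0 (SAP 7.10.1) | if a dose was reported | never: no dose exists |
| Day counts toward the 3 days (SAP 7.10.6.1) | dose or symptom | symptom only |
| Fully symptom-free week | derived as 0 | not derived |
| Responder status (SAP 7.4.2) | responder | non-responder, if these weeks are analysed |

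A derived follow-up week holds at least 3 symptoms on at least 3 days. Divided by symptom days, its all-symptom mean is at least 1; divided by 7, at least 3/7 = 0.43. A 100% all-symptom reduction is therefore impossible in a follow-up week under either denominator. A day with only mild symptoms has an entry, so it still gives a moderate/severe frequency of 0.

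**2. Single-week examples**, dividing by non-missing days. Baseline is the entry threshold, 50/7 = 7.14/day (Protocol 4.1).
- 2 symptoms on 3 days, 4 symptom-free days: true 6/7 = 0.86 (88% reduction); under the rule 6/3 = 2.00 (72%).
- 4 symptoms on 3 days, 4 symptom-free days: true 12/7 = 1.71 (76%); under the rule 12/3 = 4.00 (44%). A 50% and 70% responder becomes a non-responder.

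**3. Expected size.** Assume daily counts of all symptoms are independent Poisson(λ). The chance that a day has an entry is p = 1 − exp(−λ). A week is missing with probability P(Binomial(7, p) < 3). The expected mean of a derived week is λ/p.

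For λ = 0.5: p = 0.393, and P(missing) = 0.030 + 0.137 + 0.267 = 0.434. The derived mean is 0.5/0.393 = 1.27.

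| True mean/day | Derived mean | Week missing |
|---|---|---|
| 0.1 | 1.05 | 97.8% |
| 0.25 | 1.13 | 81% |
| 0.5 | 1.27 | 43% |
| 1 | 1.58 | 7% |
| 2 | 2.31 | 0.1% |
| 5 | 5.03 | about 0% |

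If the sum is divided by 7 instead, the missing column is unchanged and only selection remains: at 0.5/day the derived weeks average 0.67.

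**4. Between arms.** Let λ vary between women as gamma with shape 1 or 2 (200,000 simulated weeks per arm), with baseline 7.14/day, division by non-missing days and underived weeks scored as non-response.

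| Shape | True arm mean | Derived mean | Missing | 50% responders, true → rule |
|---|---|---|---|---|
| 1 | 1 | 1.94 | 38% | 97% → 59% |
| 1 | 5 | 5.68 | 10% | 52% → 41% |
| 2 | 1 | 1.76 | 27% | 99% → 72% |
| 2 | 5 | 5.25 | 2% | 43% → 39% |

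A true arm difference of 4.0/day reads 5.68 − 1.94 = 3.74 or 5.25 − 1.76 = 3.49. The responder difference falls from 97 − 52 = 45 points to 59 − 41 = 18 (shape 1), and from 99 − 43 = 56 to 72 − 39 = 33 (shape 2).

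**5. Can the order of arms reverse?** For derived means at fixed rates, no: λ/(1 − exp(−λ)) rises with λ. For responder rates, yes. At 0.1/day only 100 − 97.8 = 2.2% of weeks are derived, so at most 2.2% can respond at any threshold. At 2/day nearly all weeks are derived, with an expected mean of 2.31, a reduction of 1 − 2.31/7.14 = 68%, so a typical week counts as a 50% response.

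**The case against.** The strongest objection is that the diary's design is not known. SAP 7.10.1 applies when there are no diary entries at all, and Protocol 8.1.1 asks for use at least twice daily. If the device stores a symptom-free entry, the day is not missing. That stands as a condition. But neither document describes such an entry, SAP 6.4 counts diary days by dose or hot flash data only, and the 3-day rule read literally would still not count it.

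Second, a mean over 7 days may imply division by 7. That would remove the inflation in derived weeks, but not the 3-day rule or the scoring of underived weeks.

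Third, the SAP never says expressly that responder models run on follow-up weeks. Its table also lists Baseline and the last on-treatment week, and time to sustained response ends with treatment. This is fair: inclusion is implied, not stated.

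Fourth, the large errors need women to stay at about 1/day or less off drug, and nothing visible in the documents shows that they would.

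A reader might also infer more than the text supports:
- That the rule would create an apparent rebound. The derived means at low rates stay far below baseline.
- That follow-up diaries serve a persistence aim. No such objective is stated.
- That the co-primary results are materially biased. They are touched only when a fully symptom-free day has no reported dose in Week 4 or 12, for example during an interruption, which Protocol 4.3 foresees. A week left underived goes to multiple imputation. The documents give no rate, so the size is unknown.
- That later on-treatment weeks after early discontinuation are lost through this rule. The window definition does that.

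**Conclusion.** The point holds for Follow-up Weeks 1-3. The SAP ties observation of a day to a dose or a symptom, and off drug only the symptom is left. A fully symptom-free follow-up week fails the 3-day rule whichever denominator is used. It becomes a non-response if the responder analyses cover follow-up weeks.

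The overstatement of low means is conditional on division by non-missing days, on no stored symptom-free entry, and on the Poisson model used for its size. The figures concern all recorded symptoms. They are upper guides for moderate/severe endpoints, where mild-only days still count as 0. Reversal of arm order is shown only for responder rates under non-responder scoring, not for means.

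This is a secondary-endpoint matter that should be put right before database lock. It does not by itself call the co-primary analysis into question.

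**What to change.** In SAP 7.10.1 and 7.10.6.1, define an observed day independently of dosing for off-drug days: any morning or evening diary entry, or a device log-in. On such a day with no symptom entered, set frequency and severity to 0 and count the day toward the 3-day rule. Apply the same definition to days of drug interruption. State whether the weekly mean divides by observed days or by 7, and whether follow-up weeks enter the responder and MMRM analyses. Do not apply non-responder imputation to follow-up weeks.

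If the device holds no evidence of symptom-free use, report follow-up weeks as two bounds, with no-entry days up to the follow-up visit taken as 0 and as missing, and adopt neither alone. Filling zeros only up to the last diary contact would not help, because a fully symptom-free woman's last contact falls at about her last dose.

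The cost is SAP wording and programming on data already collected, with no added visits. The downside is that some abandoned-diary days will be read as 0 in one bound; the other bound shows how much that matters.

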5.3 Per Protocol Analysis Sets (PPS)

The PPS comprises the subset of subjects from the FAS who are treated according to the protocol without any major deviations. A full detail of inclusions and exclusions from Per Protocol Analysis Set - Week 4 (PPS4) and Per Protocol Analysis Set - Week 12 (PPS12) will be in the classifications specifications and finalized before unblinding.

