5.3.1 Reasons for Exclusion From PPS4

The following reasons may lead to subject's exclusion from PPS4:

- No measurement of the primary efficacy endpoint available at Week 4.
- <85% interactive diary compliance during the 4 week treatment period.
- Treatment compliance less than or equal to 85% between randomization and Week 4.

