5.3.2 Reasons for Exclusion From PPS12

The following reasons may lead to subject's exclusion from PPS12:

- No measurement of the primary efficacy endpoint available at Week 12.
- <85% interactive diary compliance during the 12 week treatment period.
- Treatment compliance less than or equal to 85% between randomization and Week 12.

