6.4 Other Variables

Duration of treatment exposure

Duration of exposure to treatment will be calculated in days, using the following formula:

$$\text{Days of exposure} = \text{date of last dose} - \text{date of first dose} + 1$$

Study drug compliance

Study drug compliance will be calculated using the following formula:

$$\text{Study drug compliance} = 100 \times \frac{\text{actual capsules consumed}}{\text{expected capsules consumed}}$$

where

$$\text{Actual capsules consumed} = \text{total capsules dispensed} - \text{total capsules returned}$$

$$\text{Expected capsules consumed} = (\text{last dose date} - \text{first dose date} + 1) \times 2 \text{ capsules per day}$$

Study drug compliance of morning dose

Study drug compliance of morning dose will be calculated using the following formula:

$$\text{Compliance of morning dose} = 100 \times \frac{\text{actual capsules consumed}}{\text{expected capsules consumed}}$$

where

Actual capsules consumed = morning capsules dispensed – morning capsules returned

Expected capsules consumed = (last dose date – first dose date +1) capsules per day

Study drug compliance of evening dose

Study drug compliance of evening dose will be calculated using the following formula:

$$\text{Compliance of evening dose} = 100 \times \frac{\text{actual capsules consumed}}{\text{expected capsules consumed}}$$

where

Actual capsules consumed = evening capsules dispensed – evening capsules returned

Expected capsules consumed = (last dose date – first dose date +1) capsules per day

Diary interaction compliance during the treatment period

Diary compliance during the treatment period will be calculated using the following formula:

$$\text{Diary interaction compliance} = 100 \times \frac{\text{actual diary days with data recorded}}{\text{expected diary days with data recorded}}$$

where

Actual diary days with data recorded = number of diary days with any morning or evening dose or hot flash data recorded from Visit 2 up to and including the last day of exposure to treatment

Expected diary days with data recorded = date of last dose – date of Visit 2 + 1

Previous and concomitant medication

Previous medication is defined as medication with at least one dose taken before the date of the first dose of study drug.

Concomitant medication is defined as medication with at least one dose taken between the date of first dose (inclusive) and the date of last dose (inclusive) of study drug.

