7.3.2 Treatment Compliance

Overall treatment compliance with the dosing schedule, compliance of morning dose, and compliance of evening dose will be examined for subjects in the SAF whose total study drug count and first and last days of treatment are known. Compliance will be calculated compared to the actual treatment period of dosing (first to last day of treatment), not to the planned treatment period.

Percent overall compliance, percent compliance of morning dose, and percent compliance of evening dose will be summarized in two ways for the SAF:

- Descriptive statistics will be presented by treatment group.
- Percent compliance will be categorized according to the following categories by treatment group:
 - Less than 50%,
 - at least 50%, less than or equal to 85%,
 - greater than 85%, less than or equal to 120%,
 - Over 120%, and
 - Unknown.

Overall treatment compliance, compliance of morning dose, and compliance of evening dose through Week 4 will be analyzed in a similar manner.

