7.4.1.2 Secondary Analysis of Co-Primary Endpoints

The primary analysis for each of the co-primary endpoints will be repeated using an ANCOVA model with treatment group as a factor and baseline measurement as a covariate.

A supportive analysis will be carried out for the co-primary efficacy endpoints based on the PPS to examine the impact of premature dropouts and/or major protocol deviations. The method used for this analysis will be identical to the primary analysis described in Section [7.4.1.1](#). The missing value imputation method for the early termination might not be applicable for the analysis on PPS since the analysis set only includes completed subjects. Week 4 analyses will be performed on PPS4, and the Week 12 analyses will be performed on PPS12.

An analysis of the primary efficacy variable by week will be conducted with mixed model for repeated measurements (MMRM) on FAS. This analysis will use a restricted maximum likelihood (REML)–based repeated-measures approach. The analyses will include the treatment group, week and smoking status (current vs. former/never) as factors and baseline measurement as a covariate, as well as an interaction of treatment by week and an interaction of baseline measurement by week. An unstructured covariance structure shared across treatment groups will be used to model the within-patient errors. The Kenward-Roger approximation will be used to estimate denominator degrees of freedom and adjust standard errors. The treatment difference will be estimated at all study weeks.

In addition, MCP-Mod analyses as described in the MCP-Mod SAP will be performed on co-primary endpoints.

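### Counting an unreturned kit as fully taken means the 85% compliance criterion cannot exclude a woman from PPS4, and it weakens the same criterion for PPS12

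*SAP*

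**What the plan says.** The imputation rule is in SAP 7.10.1: "For study drug compliance, the capsules returned will be imputed to 0 at the visit if no bottle was returned for a visit". SAP 6.4 computes compliance as capsules consumed over capsules expected. Consumed is dispensed minus returned, and expected is two per day from first to last dose. The calculation is repeated for each bottle; the morning version begins "Actual capsules consumed = morning capsules dispensed" and subtracts the morning capsules returned. Protocol 5.5.4 fixes the supply at a morning and an evening bottle of 34 capsules each, assigned at Day 1, Week 4 and Week 8.

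SAP 5.3 describes the per-protocol sets as FAS women "treated according to the protocol without any major deviations". The listed reasons that may lead to exclusion include "Treatment compliance less than or equal to 85% between randomization and Week 4" (PPS4) and "Treatment compliance less than or equal to 85% between randomization and Week 12" (PPS12), next to a missing endpoint and diary compliance below 85%. There is no upper compliance limit. The diary numerator in SAP 6.4 is the "number of diary days with any morning or evening dose or hot flash data recorded". SAP 7.3.2 tabulates compliance for women "whose total study drug count and first and last days of treatment are known" and provides rows for over 120% and for Unknown.

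**The concern.** Imputing zero returns assumes the highest intake the kit allows, in exactly the case where the evidence on intake is missing. The bottles are overfilled on purpose: correct dosing for 25 to 31 days leaves 34 - 25 = 9 down to 34 - 31 = 3 capsules in each. So the rule overstates intake even for a fully adherent woman who is on schedule. Because the exclusion criterion is one-sided, the overstatement can only help a woman pass.

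At stake is the purpose of the per-protocol analysis, which SAP 7.4.1.2 gives as "to examine the impact of premature dropouts and/or major protocol deviations". If poorly adherent women stay in, the PPS resembles the FAS more closely and is a weaker check. That would be expected to dilute a real difference, not create one. The descriptive compliance table is inflated as well.

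**Working it through.** The documents give no compliance figure under the imputation, so there is none to reproduce.

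**Inputs.** 68 capsules per kit (Protocol 5.5.4); two expected per day (SAP 6.4); exclusion at 85% or less (SAP 5.3.1, 5.3.2); visits within 3 days of schedule (Protocol 6.3). With the Week 4 visit targeted at Day 29 (SAP 7.10.6.1), the first kit covers 25 to 31 days before the visit. I assume the SAP 6.4 formula also serves for compliance through Week 4, as SAP 7.3.2 implies.

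**PPS4, first kit not returned.** Computed compliance = 68 / (2 x days):

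| Dosing days | Computed compliance | Criterion |
|---|---|---|
| 25 | 68/50 = 136% | passes |
| 28 | 68/56 = 121% | passes |
| 31 | 68/62 = 110% | passes |
| 36 | 68/72 = 94.4% | passes |
| 39 | 68/78 = 87.2% | passes |
| 40 | 68/80 = 85.0% | excluded |

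Actual intake does not enter the calculation. With a proper count at 28 days she would need more than 0.85 x 56 = 47.6, that is 48 capsules.

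**PPS12, one kit never returned, 84 days.** Expected 168; 0.85 x 168 = 142.8, so 143 are needed. The lost kit supplies 68, leaving 143 - 68 = 75 from the other two.

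- Lost kit covered 28 days: 75 / (168 - 56) = 75/112 = 67.0%.
- Lost kit covered 22 days: 75 / (168 - 44) = 75/124 = 60.5%.
- Lost kit covered 34 days: 75 / (168 - 68) = 75/100 = 75.0%.
- Nothing taken from the lost kit: true overall intake 75/168 = 44.6%.

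The 22 and 34 days are the extremes for the middle kit when the visits at either end fall at opposite limits of the window (28 - 6 and 28 + 6).

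**Diary criterion as a safeguard.** It is met by any entry on 24 of 28 days (85.7%) or 72 of 84 days (85.7%); 23/28 = 82.1% and 71/84 = 84.5% fail. It catches a woman who stops dosing and stops making entries. It does not catch one who skips capsules but keeps recording. As an assumed example, a woman takes only the morning capsule for 28 days, makes daily entries and does not bring back the first kit. Her true intake is 28/56 = 50%, her diary compliance 100% and her computed compliance 121%.

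**Over-120% row.** It would show an unreturned first kit at 28 days (121%) but not at 29 (68/58 = 117%), and no per-protocol criterion refers to it.

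**The case against.** The strongest objection is that this formula does not decide per-protocol membership alone. The listed reasons are conditional, and the detailed criteria are in the Classification Specifications, which are not available here. SAP 1 provides for a data review before hard lock to verify the data used for classification. Protocol 5.5.4 has sites compare returned counts with ePRO dose entries, and Protocol 5.5.5 requires return discrepancies to be explained and documented. In the morning-only example, 28 evening entries would be missing from records that sites must review. All of this stands, and it limits the consequence. It does not correct the formula, which uses no ePRO dose records.

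The rule also works visit by visit. A kit brought back later could correct PPS12 if it is then counted, so the PPS12 figures need a kit that is never returned. The wording does not say that PPS4 would be corrected.

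A reader might infer that an unreturned kit guarantees entry to PPS4. The documents do not support that: treatment compliance is one criterion among several. Nor is 67% a new threshold for overall adherence. It is the share needed from the two returned kits when the lost kit covered 28 days.

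A reader might also take the Unknown row in SAP 7.3.2 as a contradiction, or as grounds for excluding such women. That goes too far. The row belongs to a descriptive table and could still serve for missing dose dates. How it fits with the imputation needs clarifying.

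**Conclusion.** The concern holds: a stated rule gives a wrong result. An unreturned first kit cannot fail the PPS4 compliance criterion before 40 dosing days, whatever was taken. One kit never returned lowers what PPS12 requires from the other two to 67%, or about 60% to 75% depending on the days the lost kit covered.

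The arithmetic assumes that both bottles of the kit are missing. SAP 7.10.1 does not say what happens when only one is, although morning and evening compliance are computed separately. If 34 were credited for a single bottle covering 28 days, PPS12 would need 143 - 34 = 109 of 140 (77.9%) from the rest.

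Importance is low. The documents give no rate of unreturned kits, so the effect on any estimate cannot be sized, and the Classification Specifications may add exclusions. A reader might infer a threat to the primary result. There is none: the co-primary analysis and the dose-testing sequence use the FAS, and membership of the FAS does not depend on compliance.

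**What to change.** Replace the zero-return imputation in SAP 7.10.1:

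- For any bottle not returned, derive capsules taken in that interval from the ePRO home-dose records plus the recorded site-supervised morning doses (Day 1, Week 4 and Week 8, per Protocol 5.5.4).
- Apply the rule per bottle, and use the actual count if the bottle comes back later.
- If neither source exists, show compliance as Unknown in the SAP 7.3.2 table and decide per-protocol membership case by case at the blinded classification review, with no automatic pass.
- Report how many women change PPS4 or PPS12 status under the return-count version.

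The cost is a few SAP sentences and a revised derivation. The SAP already relies on diary dose reports for zero-symptom days (7.10.1) and for a missing last dose date (7.10.4). The main drawback is that self-reported doses may be under-recorded, so a few adherent women could drop out of the PPS; the status-change count would show how many. The SAP should also name where supervised doses are recorded, because the ePRO requirement covers home intake. Leaving them out would cost an adherent woman about 2 percentage points: 49/50 = 98.0% at 25 days, 55/56 = 98.2% at 28 days, 165/168 = 98.2% at 84 days.
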